2.5.3 Handling of missing values/censoring/discontinuation

Missing data will not be imputed for primary endpoints.

Novartis	Confidential	Page 17 of 34
SAP v1.1		CAMG334ADE03

For every patient, it can be determined whether he/she discontinued for AE-related reasons. Non-AE-related discontinuations or losses to follow up will not be counted as AE-related discontinuations. AE-related discontinuations are counted as events, discontinuation due to other reasons are not counted as events.

2.5.4 Sensitivity analyses

The primary analysis will also be conducted within the subgroups defined by sex, disease severity (MMD/MHD) at baseline and prior prophylactic treatment failure status (naïve vs. prior treatment failures).

2.5.5 Supplementary analyses

Not applicable

2.6 Analysis supporting secondary objectives

The secondary objective of the study is to evaluate the long-term tolerability of 70 and 140 mg erenumab in patients with episodic or chronic migraine.

2.6.1 Secondary endpoint(s)

The secondary endpoints are the proportion of patients discontinuing open-label treatment epoch due to AE and the proportion of patients discontinuing open-label treatment epoch due to non-AE reasons.

2.6.2 Statistical hypothesis, model, and method of analysis

Summary statistics for the proportion of patients discontinuing open-label treatment epoch due to AE and the proportion of patients discontinuing open-label treatment epoch due to non-AE reasons will be presented.

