## 12.8.2 **Secondary endpoint(s)**

The calculation of effect size and precision for the secondary endpoints is based on the proportion of study discontinuation rates in the three-year open-label phase II study 2012017. 4.2% of 383 patients discontinued this trial due to adverse events. Table 2 shows the effect size and precision for the proposed study with at least 500 patients.

Sample size	Proportion any AE	Precision (+/-)
500	5%	1.9%
	10%	2.6%
	15%	3.1%

Table 2: Proportion of event and precision secondary endpoint: AE-related discontinuation

Among the non-AE related study discontinuations the group 'upon patient request' was particularly high at the time point of erenumab marketing authorization. 68 patients requested study discontinuation in the first two years of the open-label study overlapping with marketing authorization. In the following 12 months 8 patients requested study discontinuation. In order to use more realistic number as basis for the effect calculations of the proposed study patient discontinuation rates after marketing authorization were utilized. This number was multiplied by three to account for the longer duration of the first part of the study and to add an additional buffer for uncertainty. This means, 24 patient requests for study discontinuation in the first two years and 8 requests in the third year were included in the calculation. Overall, this results in a discontinuation rate due to any non-AE reasons of 22.2%. Table 3 shows the estimated event rates and precisions for this secondary endpoint.

Table 3: Proportion of event and precision secondary endpoint: non AE-related discontinuation

Sample size	Proportion any AE	Precision (+/-)
500	15%	3.1%
	20%	3.5%
	25%	3.8%

In conclusion a study population of at least 500 patients was found to be sufficient for the secondary endpoints with an adequate range in precision.

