2.5.2 Statistical hypothesis, model, and method of analysis

The primary analyses will be conducted dividing the number of AEs by the time under treatment and standardizing it per 100 person-years. Exact Pearson-Clopper confidence intervals for single proportions will be calculated in order to evaluate the precision of the estimated parameter. No formal hypotheses testing will be conducted.

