2.12 Biomarkers

Not applicable

3 Sample size calculation

In general, the 750 subjects randomized for clinical trial CAMG334ADE01 will be eligible for participation in the open-label study. It is estimated that approximately 75% to 85% of the study population meaning 563~638 subjects will enroll in the open-label study thus allowing the collection of long-term safety, efficacy and quality of life data of a large group of patients.

In the three-year open-label phase II study 20120178 the proportion of patients reporting at least one AE was 87%. Based on this finding event rates and precisions were calculated for the proposed 128-week trial for the primary endpoint. In conclusion a study population of at least 500 patients was found to be sufficient for the primary endpoint with an adequate range in precision.

The calculation of effect size and precision for the secondary endpoints is based on the proportion of study discontinuation rates in the three-year open-label phase II study 2012017. 4.2% of 383 patients discontinued this trial due to adverse events. Effect size and precision for the proposed study with at least 500 patients were calculated. In conclusion a study population of at least 500 patients was found to be sufficient for the secondary endpoints with an adequate range in precision.

Novartis	Confidential	Page 22 of 34
SAP v1.1		CAMG334ADE03

4 Change to protocol specified analyses

Contrary to what was stated in the protocol, an interim analysis will be conducted. For details please refer to section 2.14 Interim analysis.

5 Appendix

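### The size of the study is judged partly on the precision of the two discontinuation proportions, but the SAP plans no interval for them and attaches its interval for a proportion to the primary AE rate

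*SAP*

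**What the plan says.** Protocol 12.8.2 tabulates a ± precision at 500 patients for each secondary endpoint. The first table is captioned "Table 2: Proportion of event and precision secondary endpoint: AE-related discontinuation" and gives ±1.9, ±2.6 and ±3.1 points at 5%, 10% and 15%. The second is captioned "Table 3: Proportion of event and precision secondary endpoint: non AE-related discontinuation" and gives ±3.1, ±3.5 and ±3.8 points at 15%, 20% and 25%. The reference rates come from an earlier three-year open-label study: "4.2% of 383 patients discontinued this trial due to adverse events", and 22.2% for non-AE reasons after an adjustment. The section concludes that "a study population of at least 500 patients was found to be sufficient for the secondary endpoints". SAP section 3 carries this over: "Effect size and precision for the proposed study with at least 500 patients were calculated". Protocol 12.8.1 makes the same argument for the proportion with any AE (Table 1).

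For the analysis of these proportions, SAP 2.6.2 offers "Summary statistics for the proportion of patients discontinuing open-label treatment epoch due to AE", and likewise for non-AE reasons. SAP 2.1 defines the presentation of categorical data as frequencies with percentages. SAP 5.4.2 only points back to section 2.6, and Protocol 12.5.1 lists the endpoints without a method.

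The interval appears under the primary endpoint. SAP 2.5.2, like Protocol 12.4.1, divides the number of AEs by time under treatment, scales to 100 person-years, and then states: "Exact Pearson-Clopper confidence intervals for single proportions will be calculated".

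**The concern.** The study has one arm and no hypothesis test, so its inferential content is estimates with their uncertainty. The two secondary endpoints are simple binomial proportions, and their interval width is part of the case that the study is large enough. As written, the plan reports them without an interval, and the method that suits them is assigned to a quantity that is not a proportion. A programmer following the SAP would leave the tolerability estimates bare and would have no valid way to carry out the interval for the primary rate. Leaving the secondary intervals unspecified also leaves their method, level and denominator open until after the data are seen.

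**Working it through.** **1. What precision means in the tables.** Inputs are N = 500 and the planning proportions p from Protocol 12.8.2. The documents give no confidence level, so 95% is an assumption to be tested. The Wald half-width is 1.96 × √(p(1−p)/500). For p = 5%: √(0.05 × 0.95/500) = 0.009747, and 1.96 × 0.009747 = 1.91 points, against ±1.9 stated. The same formula gives every row:

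| Endpoint | p (count of 500) | Stated ± | Wald ± | Exact 95% interval | Exact half-width |
|---|---|---|---|---|---|
| AE-related | 5% (25) | 1.9 | 1.91 | 3.26% to 7.29% | 2.02 |
| AE-related | 10% (50) | 2.6 | 2.63 | 7.51% to 12.97% | 2.73 |
| AE-related | 15% (75) | 3.1 | 3.13 | 11.98% to 18.44% | 3.23 |
| Non-AE | 15% (75) | 3.1 | 3.13 | 11.98% to 18.44% | 3.23 |
| Non-AE | 20% (100) | 3.5 | 3.51 | 16.58% to 23.78% | 3.60 |
| Non-AE | 25% (125) | 3.8 | 3.80 | 21.26% to 29.04% | 3.89 |

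All six stated values reproduce. The four rows of Table 1 do too (4.02, 3.51, 3.13 and 2.63 against 4.0, 3.5, 3.1 and 2.6). A 90% level would give 1.60, 2.21 and 2.63 for Table 2, which does not match. Wilson half-widths also match after rounding. So the stated precision is a 95% confidence-interval half-width.

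**2. The intervals that are not planned.** Clopper-Pearson limits for x events in n patients are the 2.5% point of Beta(x, n−x+1) and the 97.5% point of Beta(x+1, n−x). The last two columns above show them. At the reference rates, 21/500 = 4.2% gives 2.62% to 6.35%, and 111/500 = 22.2% gives 18.63% to 26.10%. Exact half-widths at 500 patients are about 0.1 point wider than the tabulated values.

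**3. Effect on the sample size.** At the lower expected enrolment of 563, the exact half-widths at the counts nearest 5%, 10%, 15%, 20% and 25% (28, 56, 84, 113 and 141) are 1.89, 2.56, 3.03, 3.39 and 3.66 points. All lie within the stated precision.

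**4. Why the interval does not fit the primary rate.** For illustration, assume 500 patients who all complete 128 weeks without a drug holiday, so person-years = 500 × 128/52.18 = 1226.5. The number of AEs per patient is also assumed.

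| AEs per patient | AEs | Rate per 100 person-years | Exact Poisson 95% interval | Clopper-Pearson on AEs/patients | Clopper-Pearson on AEs/person-years |
|---|---|---|---|---|---|
| 1 | 500 | 40.8 | 37.3 to 44.5 | AEs equal patients; upper limit is 1 | 38.0 to 43.6 |
| 2 | 1000 | 81.5 | 76.6 to 86.7 | undefined | 79.2 to 83.6 |
| 4 | 2000 | 163.1 | 156.0 to 170.4 | undefined | undefined |

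Where the last column can be computed it has no binomial meaning, because a person-year is not a trial with one yes-or-no outcome. The Poisson figures treat AEs as independent and would be too narrow if AEs cluster within patients. SAP 2.1.1.1 defines the exposure-adjusted rate differently, as patients with an AE over patient-years up to the first event. That is still a rate, so the mismatch remains under either definition.

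**The case against.** **The intervals can be recovered.** The output will give counts and percentages, and SAP 2.3.1 reports the size of each analysis set, so anyone can compute a binomial interval. This stands. A reader might infer that the tolerability results could not be set against the 4.2% and 22.2% planning figures. The documents do not support that: the comparison can be made from the counts, and none is planned. Nor is 22.2% an observed benchmark, because Protocol 12.8.2 replaces early patient-request withdrawals with a later figure multiplied by three, partly as a buffer.

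**Tables 2 and 3 do not fix the sample size.** A reader might infer that they do. Enrolment is bounded by the 750 patients of the parent trial, with 563 to 638 expected, and Table 1 is an equal basis for calling 500 sufficient. The discontinuation tables are one part of an adequacy check.

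**The protocol may already extend the interval.** Protocol 12.4.3 repeats the primary analysis for all-cause instead of AE-related treatment discontinuation, and Protocol 12.4.2 and SAP 2.5.3 count AE-related discontinuations as events under the primary endpoint. This wording suggests that the interval was meant for a discontinuation proportion. It does not close the gap, because the SAP moves the all-cause repeat to 2.6.4 without taking the interval along.

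**The primary-rate interval is a separate defect.** This is fair, in that adding intervals to SAP 2.6 alone would leave SAP 2.5.2 wrong. Both sections need the change.

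**Conclusion.** The point holds as a mismatch between the planned analysis and the basis on which the study's size was judged. The binomial endpoints get no interval, and a binomial interval is placed on a rate. The gap for the secondary endpoints is one of reporting: roughly ±1.9 points around 4.2% and ±3.7 points around 22.2% at 500 patients would go unshown, but they are recoverable from the counts. The fault in SAP 2.5.2 goes further, because the specified method has no valid application to the specified estimator. It should be corrected before analysis, but it does not threaten the design: the sample size and all point estimates stay as they are. The conclusion assumes a 95% level, which the documents do not state but which reproduces all ten tabulated values. The person-year illustration rests on assumed AE counts and full follow-up, and serves only to show where the binomial interval breaks down.

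**What to change.** - **SAP 2.6.2 and 2.6.4:** specify two-sided 95% Clopper-Pearson intervals for the AE-related, non-AE and all-cause discontinuation proportions, and name the Safety Set as denominator. SAP 2.6 names no analysis set, and the general rule in SAP 2.1 drops missing values from percentages. The Full Analysis Set is identical to the Safety Set, so naming it settles the denominator without altering any result.
- **SAP 2.5.2:** replace the Clopper-Pearson interval with one suited to a rate, at a stated level. Use an exact Poisson interval if each patient counts once, or a method that allows for repeated AEs within a patient if all AEs count. SAP 2.1.1.1 and 2.5.2 describe these two estimators differently, so the SAP must first say which is primary.
- **SAP section 4:** record the second change as a departure from Protocol 12.4.1.

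The cost is a few sentences and an interval column in the affected tables. No additional data are needed. The exact intervals will be about 0.1 point wider than the protocol's tabulated values at 500 patients, and within them at the expected enrolment of 563 or more.

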2.6.3 Handling of missing values/censoring/discontinuation

For every patient, it can be determined whether he/she discontinued for AE-related reasons. AE-related discontinuations are counted as events. Discontinuation due to the other reasons as non-AE-related treatment discontinuations or losses to follow up should not be counted as event.

2.6.4 Sensitivity analyses

The secondary analysis will also be repeated for all-cause treatment discontinuations (instead of AE-related).

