#### 9.1.3 **Lost to follow-up**

For subjects whose status is unclear because they fail to appear for study visits without stating an intention to discontinue or withdraw, the investigator must show "due diligence" by documenting in the source documents steps taken to contact the subject, e.g. dates of telephone calls, registered letters, etc. A subject should not be considered as lost to follow-up until due diligence has been completed or until the end of the study.

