2.6.5 Supplementary analyses

Not applicable

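### The planned all-cause repeat cannot show whether the AE-related discontinuation proportion depends on scoring patients lost to follow-up as non-events; one worst-case row would

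*SAP*

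**What the plan says.** SAP 2.6.1 names two secondary endpoints: the share of patients who stop the open-label epoch because of an AE, and the share who stop for any other reason. SAP 2.6.2 gives both summary statistics only.

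SAP 2.6.3 sets the counting rule. Its premise is "For every patient, it can be determined whether he/she discontinued for AE-related reasons". It then says: "Discontinuation due to the other reasons as non-AE-related treatment discontinuations or losses to follow up should not be counted as event". It does not say whether losses to follow-up belong to the non-AE proportion or to neither.

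SAP 2.6.4 contains one sensitivity analysis: "The secondary analysis will also be repeated for all-cause treatment discontinuations (instead of AE-related". SAP 2.6.5 plans no supplementary analyses, and SAP 5.1 rules out imputing missing endpoints.

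The protocol is less certain about cause. Section 9.1.3 introduces loss to follow-up with the words "For subjects whose status is unclear because they fail to appear for study visits without stating an intention to discontinue or withdraw". Section 9.1.1 asks the investigator for a reasonable effort to learn why treatment was stopped, which does not guarantee an answer.

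**The concern.** A patient who disappears has no established reason for stopping. SAP 2.6.3 nevertheless places that patient with those known not to have stopped for an AE. The rule works in one direction: if some lost patients did stop because of an AE, the reported proportion is too low, and no lost patient can make it too high.

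A sensitivity analysis should vary the assumption in doubt. Here that assumption is the cause assigned to patients whose cause is not known. The all-cause repeat removes cause from the endpoint altogether. AE-related discontinuation is one of only two endpoints for the tolerability objective and is expected to be a small proportion, so a modest number of unknown-cause stops could matter relative to its planned precision. As the plan stands, a reader of the report could not tell.

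**Working it through.** **Inputs**
- AE-related discontinuation, planning value: 4.2% of 383 patients (Protocol 12.8.2).
- Non-AE discontinuation, planning value: 22.2% (Protocol 12.8.2).
- Planning sample size 500, with precision ±1.9 points at a proportion of 5% (Protocol 12.8.2, Table 2).
- Loss-to-follow-up rate: not in the documents. I assume 1%, 2% and 5%.

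**Step 1: reproduce the stated precision.** The two-sided 95% Wald half-width is 1.96 × √(p(1 − p)/n). At p = 0.05 and n = 500 it is 1.96 × √(0.05 × 0.95/500) = 0.0191, or 1.9 points, as in Table 2. This corresponds to 0.019 × 500 = 9.5 patients. The exact 95% interval for 25 of 500 is 3.3% to 7.3%.

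**Step 2: what the all-cause repeat responds to.** Let A be recorded AE stops, B recorded non-AE stops, L stops of unknown cause (lost to follow-up or no recorded reason), and N the number of patients. Suppose k of the L patients in truth stopped for an AE, with 0 ≤ k ≤ L.
- Reported AE proportion: A/N.
- True AE proportion: (A + k)/N.
- Shortfall: k/N, never negative and at most L/N.
- All-cause proportion with losses included: (A + B + L)/N. It does not contain k.

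If L sits inside the non-AE proportion, all-cause is the sum of the two reported proportions. If L sits in neither, it is that sum plus L/N. In both cases it is the same for every value of k.

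On the planning values, with losses inside the non-AE proportion, all-cause = 4.2% + 22.2% = 26.4%, or 132 of 500 (exact 95% interval 22.6% to 30.5%). This is the ceiling reached by calling every stop AE-related, about six times the 4.2% it is meant to support (26.4/4.2 = 6.3).

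**Step 3: what a targeted worst case would show.** Take N = 500 and A = 25 (5.0%), and set k = L.

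| Assumed lost | Patients lost | Worst-case AE proportion | Exact 95% interval |
|---|---|---|---|
| 1% | 5 | (25 + 5)/500 = 6.0% | 4.1% to 8.5% |
| 2% | 10 | (25 + 10)/500 = 7.0% | 4.9% to 9.6% |
| 5% | 25 | (25 + 25)/500 = 10.0% | 7.5% to 13.0% |

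At 1% lost the largest possible shift, 1.0 point, is below the 1.9-point precision. At 2% the shift (2.0 points) about equals it, and would need 1.9/2 = 95% of the lost patients to be AE stops. At 5%, 1.9/5 = 38% of them would be enough. Starting instead from the 4.2% planning rate (21 of 500), the worst cases are 5.2%, 6.2% and 9.2%.

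**The case against.** Several points on the other side stand.

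- **The rule is stated openly and can be applied.** SAP 2.1.1.4 takes AE-related discontinuation from a flag on the Treatment Completion page and adds deaths, so every patient can be assigned a value. Protocol 9.1.3 speaks of missed visits and due diligence, not of AE causality, and 9.1.1 provides for contact attempts and AE collection after treatment stops. This reduces the number of unknown causes. It does not make the cause known for a patient who is never reached.
- **The AE page is already tabulated.** SAP 2.1.1.4 defines AEs leading to dose adjustment by action taken, including interruption and withdrawal, and SAP 2.8.1 summarises these and lists AEs leading to permanent discontinuation. Much of a cross-check between pages is therefore planned.
- **All-cause is not empty.** It comes from Protocol 12.4.3 and does bound the answer, though loosely.
- **Nothing formal depends on it.** The trial has one arm, and the endpoint is descriptive, with no test or threshold.

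Two stronger readings are tempting and should be resisted. A reader might treat the whole 22.2% as a pool of doubtful stops and note that 1.9/22.2 = 8.6% of it would use up the precision. Protocol 12.8.2 presents 22.2% as a rate for non-AE reasons, not as unknown cause. It is partly constructed, with 24 + 8 = 32 patient requests, part of which is a deliberate buffer; on 383 patients that is 8.4 of the 22.2 points. Nothing shows that any share of it is misclassified. A reader might also say that all-cause is exactly the sum of the two endpoints. That holds only if losses sit in the non-AE proportion, which SAP 2.6.3 leaves open. In addition, 2.6.1 counts stopping the epoch while 2.6.4 counts stopping treatment.

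**Conclusion.** The point holds in a limited form. SAP 2.6.3 claims more knowledge of cause than the protocol supports, its rule for losses can err only towards a lower AE proportion, and the one sensitivity analysis does not respond to that error. The all-cause ceiling of about 26.4% against 4.2% is too wide to reassure.

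The documents do not show that the AE proportion will be understated by any particular amount. That depends on a loss-to-follow-up rate they do not give, and the worst-case figures are bounds under assumed rates, not estimates. If about 1% are lost, the issue is smaller than the stated precision; if 5% are lost, the worst case doubles the 5.0% proportion. This is a cheap improvement to a descriptive endpoint, not a flaw in the trial's main conclusion.

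**What to change.** In SAP 2.6.3, limit the statement that cause can be determined to patients with a recorded reason, and say which proportion, if either, holds losses to follow-up.

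In SAP 2.6.4, keep the all-cause repeat and add one worst-case row that counts patients lost to follow-up or without a recorded reason as AE-related. Use all Safety Set patients as the denominator, because the general rule in SAP 2.1 leaves missing values out of percentages.

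Do not override recorded reasons such as patient decision or consent withdrawal. An AE present at the time of stopping need not be the cause, and Protocol 10.1.1 records interruption and withdrawal as one combined action. At most, list patients with such reasons who also have an AE with the action drug withdrawn, as a consistency check, if the eCRF separates the two actions as SAP 2.1.1.4 implies.

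The cost is a few words and one table row from data already collected. The downside is a sensitivity figure less favourable than the main one, which should be labelled as a bound.

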2.6.5 Supplementary analyses

Not applicable

2.8 Safety analyses

Safety analyses will be based on safety data set (SAF). Missing data will not be imputed for safety endpoints.

2.8.1 Adverse events (AEs)

In the frame of safety analysis the following treatment-emergent AE types will be considered:

- Any AE
- Study treatment related AE
- AE leading to study treatment discontinuation
- AE leading to dose adjustment (including study treatment discontinuation)
- Serious AE (SAE)
- Study treatment related SAE
- SAE leading to study treatment discontinuation
- Death

The Medical Dictionary for Regulatory Activities (MedDRA) version 24.1 or later will be used to code all adverse events (AE) to a system organ class (SOC) and a preferred term (PT).

Novartis	Confidential	Page 19 of 34
SAP v1.1		CAMG334ADE03

The SOCs will be presented in the alphabetic order and PTs will be ordered within the SOCs by decreasing order of frequency.

The number (and percentage) of subjects with treatment emergent adverse events (events started after the first dose of study medication or events present prior to start of treatment but increased in severity based on preferred term) will be summarized in the following ways:

- by primary system organ class and preferred term.
- by primary system organ class, preferred term and maximum severity
- by Standardized MedDRA Query (SMQ) and preferred term

If a patient reported more than one adverse event with the same PT, the adverse event with the greatest severity will be presented. If a patient reported more than one adverse event within the same primary system organ class, the patient will be counted only once with the greatest severity at the system organ class level, where applicable.

The overview of adverse events occurring during treatment will additionally be presented by starting dose (70mg/140mg).

All AEs, deaths (see see section 2.8.2 Deaths for details), SAEs and AEs leading to permanent study drug discontinuation will be listed separately.

